4.5.6 Treatment of Infusion Related Reactions (nivolumab/brentuximab vedotin)

Infusion-related reactions may occur during the infusion of study treatment(s). The infusion should be administered at a site properly equipped and staffed to manage anaphylaxis should it occur. All supportive measures consistent with optimal patient care should be given throughout the study according to institutional standards. Supportive measures may include extending the infusion time and/or administering medications for infusion-related reactions.

Infusion or hypersensitivity reactions may occur to either brentuximab vedotin or nivolumab. If such a reaction were to occur, it might manifest with fever, chills, rigors, headache, rash, pruritus, arthralgias, hypotension, hypertension, bronchospasm, or other allergic-like reactions. Infusion reactions should be graded according to NCI CTCAE (Version 4.03) guidelines.

Subjects who experience a Grade 1 or Grade 2 infusion-related reaction should be premedicated for subsequent infusions. Premedication should be given at least 30 minutes prior to dosing study drug(s) and should include an antihistamine and corticosteroid. Recommended doses are: diphenhydramine 25-50 mg IV (or equivalent) and methylprednisolone 40 mg IV (or equivalent). In addition, acetaminophen/paracetamol 325 to 1000 mg and ranitidine 50 mg IV may be given. If the onset of a reaction occurs during an infusion, the infusion may be interrupted for treatment of the infusion-related reaction, including treatment with antihistamines, corticosteroids, and/or bronchodilator therapy, as appropriate. Subjects who experience a Grade 3 infusion-related reaction to brentuximab vedotin or nivolumab may potentially receive additional treatment with the study drug(s) at the discretion of the investigator after discussion with the sponsor.

If anaphylaxis or a Grade 4 infusion-related reaction occurs, administration of the implicated agent(s) (brentuximab vedotin and/or nivolumab) should be immediately and permanently discontinued.

In case of late-occurring hypersensitivity symptoms to nivolumab (eg, appearance of a localized or generalized pruritus within 1 week after nivolumab treatment), symptomatic treatment may be given (eg, oral antihistamine or corticosteroids).

4.5.7 Management of Suspected PML

Signs and symptoms of PML may include altered mental status, motor deficits such as hemiparesis or ataxia, visual disturbances, or higher cortical dysfunction such as dysphasia or agnosia. See the brentuximab vedotin (IB) for further details.

If PML is suspected, hold further dosing of brentuximab vedotin and nivolumab and undertake a diagnostic work-up including (but not limited to):

- Neurologic examinations, as warranted
- Brain radiologic features by magnetic resonance imaging (MRI)
- PCR analysis: John Cunningham virus (JCV) DNA detectable in cerebrospinal fluid

If PML is confirmed, permanently discontinue treatment with brentuximab vedotin and nivolumab.

4.5.8 Guidelines for Assessment and Initial Management of Tumor Lysis Syndrome

The possibility of tumor lysis syndrome cannot be ruled out for the subjects with lymphoma. Therefore, adequate management such as hydration and/or the use of allopurinol is recommended in the subjects who have risk factor of potential tumor lysis syndrome, for example the subjects with high tumor burden, reflected by high serum LDH levels, or bulky disease, or those with preexisting renal failure.

4.5.9 Treatment Beyond Disease Progression

4.5.9.1 Circumstances in which post-progression treatment is permitted

Subjects meeting progression defined by relapsed disease (after CR) or progressive disease (after PR, SD) per 2014 Lugano Classification & the Lymphoma Response to Immunomodulatory therapy Criteria (LYRIC)⁸⁵ for DLBCL/PTCL/PMBL/MGZL ([Appendix 2](#)) or modified Severity Weighted Assessment Tool (mSWAT) and Global Response Score in CTCL criteria ([Appendix 4](#)) may continue receiving study medication beyond investigator-assessed progression as long as they meet the following criteria:

- Investigator-assessed clinical benefit
- Stable performance status
- Treatment beyond progression will not delay an imminent intervention to prevent serious complications of disease progression
- Subjects will be re-consented for treatment beyond progressive disease
- Tolerance of study drug.

The decision to continue treatment beyond investigator-assessed progression should be discussed with the BMS Medical Monitor and documented in the study records. The assessment of clinical benefit should take into account whether the subject is clinically deteriorating and unlikely to receive further benefit from continued treatment.

4.5.9.2 Assessment Schedule for the Subjects with Post-progression Treatment

The subject should continue to receive monitoring according to the Lymphoma Response to Immunomodulatory therapy Criteria (LYRIC) a minimum of 12 weeks On-Treatment Assessments on [Table 5.1-2](#). Radiographic assessment described in [section 5.4.1](#) should be performed when subjects continue post progression treatment as outlined in [appendix 2](#).

4.5.9.3 Discontinuation due to “Further Progression”

Subjects should discontinue study therapy upon evidence of further progression, defined as an additional 10% or greater increase in tumor burden volume from time of initial progression (including all target lesions and new measurable lesions, increase in tumor burden without a 5mm absolute increase does not require discontinuation) from previous PET-CT, CT and/or MRI.

- The tumor burden volume from time of initial progression should be used as the reference baseline for comparison with the post-progression assessment.
- New lesions are considered measurable at the time of initial progression if the long axis is more than 15 mm regardless of the short axis. Increase in tumor burden without a 5mm absolute increase does not require discontinuation.
- Any new lesion considered non-measurable at the time of or after initial progression may become measurable and therefore included in the tumor burden determination.

4.5.9.4 Efficacy Assessment for Subjects who Discontinue Study Drug during Post-Progression Treatment

When subjects stop post-progression treatment, no additional radiographic assessment will be required and they will continue in the follow-up phase of the study ([Table 5.1-3](#)). The subjects who proceed to allogeneic SCT or ASCT will be followed with specific tumor assessment on day 100, at 6 months, 1 year and every year thereafter from the date of stem cell infusion until the first non-CR after SCT is documented.

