- 3) Increase in FDG uptake of one or more lesion(s) without a concomitant increase in lesion size or number (IR(3))

It is possible that, at a single time point a subject could fulfill criteria for both IR(1 or 2) AND IR(3): for example, there could be a new FDG-avid lesion in the absence of overall progression (IR(2)), and, at the same time, increase in FDG uptake of a separate lesion (IR(3)). In such cases, the designation of IR(1 or 2) should take priority (eg, IR(2))

Follow-up of IR

- 1) In patients categorized as having any of the above types of IR, it is mandatory to obtain a repeat imaging after an additional 12 weeks (or earlier if clinically indicated). At that time, response should be re-evaluated and the patient should be considered to have true PD if the SPD of target lesion has increased further, with the considerations below:
- 2) In the case of IR(1), the comparison should be between the first IR(1) and the current SPD, with an increase of >10% constituting PD. In addition there should be an increase of > 5 mm (in either dimension) of at least one lesion for lesions < 2 cm, and 10 mm for lesions > 2 cm, to be consistent with the Lugano classification (3)(Table 2). The 10% threshold is empiric but designed to account for variability in measurement (37), especially when taken along with the minimum increase. If the target SPD increase is < 10%, the response would still be categorized as IR(1), and the patient could continue treatment until a subsequent scan shows either true PD (> 10% increase from first IR(1) time point and an increase of > 5mm in either dimension of at least one lesion) or response (>50% decrease from baseline). In this situation, it is reasonable to repeat imaging in 4-8 weeks of the original IR(1) timepoint to ensure absence of significant further increase.
- 3) In the case of IR(2), the new or growing lesion(s) (unless biopsy proven to be benign) should be added to the target lesion(s), up to a total of no more than 6 total lesions. If the SPD of the newly defined set of target lesions has increased > 50% from the nadir value which may precede the IR time point. The patients is considered to have PD.
- 4) In the case of IR(3), since inflammatory responses may result in an increase in the standardized uptake value of a lesion, the patient will not be considered to have PD unless there is evidence of PD by an increase in lesion size or the development of new lesions, as noted above

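### The stopping rule for treatment beyond progression (Protocol 4.5.9.3) resembles only the IR(1) rule in Appendix 2, and on the same scan can give the opposite answer to the IR(2) rule or the IR(1) 10 mm minimum

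*Protocol*

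**What the plan says.** Section 4.5.9.3 gives one rule for every subject treated past progression. Further progression is "defined as an additional 10% or greater increase in tumor burden volume from time of initial progression". The rise counts all target lesions and new measurable lesions, and "increase in tumor burden without a 5mm absolute increase does not require discontinuation". A bullet then fixes the reference: "The tumor burden volume from time of initial progression should be used as the reference baseline for comparison with the post-progression assessment". The defining sentence, however, ends by naming the previous PET-CT, CT or MRI as the comparator. Tumor burden volume is not defined. The section does not mention LYRIC or IR type.

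Section 4.5.9.1 defines the progression that opens post-progression treatment by Lugano and LYRIC for the DLBCL, PTCL, PMBL and MGZL cohorts. Section 4.5.9.2 says of these subjects: "The subject should continue to receive monitoring according to the Lymphoma Response to Immunomodulatory therapy Criteria (LYRIC". It adds that radiographic assessment "should be performed when subjects continue post progression treatment as outlined in" Appendix 2. Table 5.1-2 also points to Appendix 2 for subjects treated beyond progression.

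Appendix 2, under follow-up of IR, decides true progression by IR type. For IR(2) the test is: "If the SPD of the newly defined set of target lesions has increased > 50% from the nadir value", on a set of at most 6 lesions. Appendix 4 repeats the IR text for CTCL, to be applied where clinically applicable.

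**The concern.** Two passages apply to the same subjects and the same scans. One decides whether treatment stops. The other decides whether an indeterminate response has become true progression, and for IR(1) it also says that the patient may stay on treatment until true progression or response. If they use different thresholds, reference scans and size measures, one scan can end treatment under one passage and leave the subject short of progression under the other.

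Three things are at stake: how long subjects are treated past progression, whether the scan that would resolve an IR is obtained, and the exploratory IR classification. On the second, section 4.5.9.4 requires no further radiographic assessment once post-progression treatment stops, apart from the transplant schedule. Appendix 2 makes repeat imaging after IR mandatory within an additional 12 weeks.

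**Working it through.** No figure in the plan needs reproducing. The rules are set side by side and then applied to assumed lesion sizes.

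| | 4.5.9.3 | Appendix 2, IR(1) | Appendix 2, IR(2) |
|---|---|---|---|
| Rise | 10% or more | more than 10% | more than 50% |
| Reference | initial progression; also the previous scan | first IR(1) scan | nadir, which may precede the IR scan |
| Measure | tumor burden volume, undefined | SPD | SPD |
| Absolute minimum | 5 mm, any lesion size | more than 5 mm (lesions under 2 cm) or 10 mm (over 2 cm); later in the same item, more than 5 mm for any lesion | none stated |
| Lesions | all target plus new measurable | target | redefined set, at most 6 |

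For IR(3), Appendix 2 does not call progression on FDG uptake alone. Section 4.5.9.3 is size-based and does not act on uptake either, so they do not clash.

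**Where the IR(2) rule and 4.5.9.3 cross.** Read tumor burden as SPD and initial progression as the IR scan. Let N be nadir SPD, I the SPD at IR, W the current SPD, and r = I/N. Section 4.5.9.3 triggers at W = 1.10 × r × N (given 5 mm growth); IR(2) triggers above W = 1.50 × N. They coincide only at r = 1.50/1.10 = 1.364. Below that, 4.5.9.3 acts first; above it, Appendix 2 does.

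**Example A, IR(2) through a new lesion.**
- Nadir: 20×20 and 30×20 mm, SPD 400 + 600 = 1000.
- IR: a new 16×12 mm lesion, SPD 1000 + 192 = 1192. The total rise is 19.2%, under 50%, so this is IR(2). The long axis exceeds 15 mm, so the new lesion is measurable under 4.5.9.3.
- Next scan: the new lesion is 22×16 mm, SPD 1000 + 352 = 1352, growth 22 − 16 = 6 mm.
- 1352/1192 − 1 = 13.4%: 4.5.9.3 met. 1352/1000 − 1 = 35.2%: IR(2) progression not met. There are three lesions, so the cap of 6 plays no part.

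**Example B, IR(2) in the other direction.**
- Nadir as in A, SPD 1000.
- IR: the first lesion is 30×28 mm, SPD 840 + 600 = 1440. That lesion grew by 840/400 − 1 = 110%, while the total rose 44.0%, so this is IR(2).
- Next scan: 31×29 and 31×20 mm, SPD 899 + 620 = 1519.
- 1519/1440 − 1 = 5.5%, with 1 mm growth: 4.5.9.3 not met. 1519/1000 − 1 = 51.9%: IR(2) progression met.

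**Example C, IR(1), lesion over 2 cm.**
- Baseline, assumed also the nadir: 25×20 mm twice, SPD 1000.
- First IR(1): 40×25 and 30×20 mm, SPD 1000 + 600 = 1600, up 60.0%.
- Next scan: 47×25 and 30×20 mm, SPD 1175 + 600 = 1775.
- 1775/1600 − 1 = 10.9%, with 7 mm growth: 4.5.9.3 met. The 10 mm minimum in Appendix 2 is not met, but its later wording of more than 5 mm is. Appendix 2 therefore gives two answers by itself.

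**The case against.** The strongest reply is that the rules act in sequence: Appendix 2 classifies IR against true progression, and 4.5.9.3 then governs stopping after progression. If initial progression means LYRIC-confirmed progression, the second rule starts where the first ends. The text does not exclude this, but does not state it either, and several places lean the other way. The IR(1) item in Appendix 2 itself speaks to continuing treatment. Sections 4.5.9.1 and 4.5.9.2 and Table 5.1-2 tie post-progression treatment to LYRIC or Appendix 2. Appendix 2 also back-dates later true progression to the IR date when no response intervened, although only for reporting. The two IR(1) minimums conflict under any reading.

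A reader might infer four stronger claims that the documents do not support:

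- *That 4.5.9.3 contradicts LYRIC as a whole.* Its 10% figure and reference match IR(1) almost exactly, and IR(3) does not clash.
- *That the protocol tells sites to base stopping on LYRIC.* It cites LYRIC for progression, monitoring and imaging. No passage says that the stopping decision follows it.
- *That the main efficacy results are compromised.* Best overall response closes at initial documented progression or subsequent therapy (Protocol 8.3.1, SAP 4.1), and DOR and PFS end at first documented progression. SAP 4.2 bases the secondary endpoints on Lugano and the Global Response Score. Protocol 5.4 does mention LYRIC in describing objective response, but the endpoint definitions do not.
- *That back-dating of IR to progression would vary by site because of 4.5.9.3.* Appendix 2 alone sets it.

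It also stands that continuing past progression must be discussed with the sponsor's medical monitor (4.5.9.1), which should limit variation between sites.

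**Conclusion.** The inconsistency is real but narrow. Section 4.5.9.3 mirrors only IR(1). It conflicts with IR(2) on threshold, reference and lesion set, in either direction depending on whether SPD at IR is below or above 1.364 times nadir, and with the IR(1) 10 mm minimum for lesions over 2 cm. Appendix 2 contradicts itself on that minimum, and Appendix 4 carries the same text. The undefined size measure, the two comparators and the unspecified initial progression add to the ambiguity.

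The IR(2) conflict and the clash between 4.5.9.3 and the 10 mm minimum rest on taking initial progression as the first Lugano progression or IR scan. The examples use assumed lesion sizes and read tumor burden as SPD. The documents do not say how many subjects will be treated past progression or how they split by IR type, so the number affected cannot be estimated. The consequences fall on treatment duration, resolution of IR and an exploratory objective; the primary ORR definition is little affected. It should be corrected.

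**What to change.** Reconcile section 4.5.9.3 with the follow-up-of-IR text in Appendices 2 and 4:

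- state which scan is the initial progression, and whether it is the only comparator;
- use one defined size measure and say which lesions it covers;
- say how 4.5.9.3 relates to each IR type, including whether it acts alongside Appendix 2 or only after LYRIC-confirmed progression;
- resolve the two IR(1) absolute minimums;
- align 4.5.9.4 with the mandatory repeat imaging after IR.

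This does not require a single reference point throughout: Appendix 2 uses the first IR(1) scan for one type and nadir for another by design. Which clinical rule applies is for the sponsor and its clinical advisers. The cost is wording in the next amendment.

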4.6 Blinding/Unblinding

Not applicable.

4.7 Treatment Compliance

Treatment compliance will be monitored by drug accountability as well as the subject’s medical record and CRF.

4.8 Destruction of Study Drug

For this study, study drugs (those supplied by BMS or sourced by the investigator) such as partially used study drug containers, vials and syringes may be destroyed on site.

Any unused study drugs can only be destroyed after being inspected and reconciled by the responsible Study Monitor unless study drug containers must be immediately destroyed as required for safety, or to meet local regulations (eg, cytotoxics or biologics).

On-site destruction is allowed provided the following minimal standards are met:

- On-site disposal practices must not expose humans to risks from the drug.
- On-site disposal practices and procedures are in agreement with applicable laws and regulations, including any special requirements for controlled or hazardous substances.
- Written procedures for on-site disposal are available and followed. The procedures must be filed with the site's SOPs and a copy provided to BMS upon request.
- Records are maintained that allow for traceability of each container, including the date disposed of, quantity disposed, and identification of the person disposing the containers. The method of disposal, ie, incinerator, licensed sanitary landfill, or licensed waste disposal vendor must be documented.
- Accountability and disposal records are complete, up-to-date, and available for the Monitor to review throughout the clinical trial period.

If conditions for destruction cannot be met the responsible Study Monitor will make arrangements for return of study drug.

It is the investigator's responsibility to arrange for disposal of all empty containers, provided that procedures for proper disposal have been established according to applicable federal, state, local, and institutional guidelines and procedures, and provided that appropriate records of disposal are kept.

4.9 Return of Study Drug

If study drug will not be destroyed upon completion or termination of the study, all unused and/or partially used study drug that was supplied by BMS must be returned to BMS. The return of study drug will be arranged by the responsible Study Monitor.

It is the investigator's responsibility to arrange for disposal of all empty containers, provided that procedures for proper disposal have been established according to applicable federal, state, local, and institutional guidelines and procedures, and provided that appropriate records of disposal are kept.

4.10 Retained Samples for Bioavailability / Bioequivalence

Not Applicable

5 STUDY ASSESSMENTS AND PROCEDURES

5.1 Flow Chart/Time and Events Schedule

Table 5.1-1: Screening Assessments (CA209436)		
Procedure	Screening Visit	Notes (Screening procedures are to occur within 28 days from first dose unless otherwise specified)
Eligibility Assessment		
Informed Consent	X	
Inclusion/Exclusion Criteria	X	All inclusion/exclusion criteria should be assessed at screening
Medical History	X	
Prior Systemic Therapy	X	
Safety Assessments		
Complete Physical Examination	X	Include assessment of lymph node areas (eg, submandibular, cervical, supraclavicular, axillary, or inguinal lymph node), abdominal organs (eg, spleen) and neurological examination Skin evaluations using m SWAT for CTCL
Physical Measurements	X	Include height, weight and ECOG Performance Status
Vital Signs and oxygen saturation	X	Temperature, BP, HR, and O ₂ saturation by pulse oximetry at rest (also monitor amount of supplemental oxygen if applicable).
Assessment of Signs and Symptoms	X	Required for the 14 days prior to first dose
Concomitant Medication Collection	X	Required for the 14 days prior to first dose,
Laboratory Tests	X	CBC with differential, Chemistry panel including LDH, AST, ALT, ALP, albumin, total bilirubin, BUN or serum urea level, uric acid, creatinine, Ca, Mg, Na, K, Cl, glucose, amylase, lipase, TSH, Free T3, Free T4 within 14 days prior to first dose. Hepatitis B surface antigen (HBV sAg), and hepatitis C antibody (HCV Ab) or HCV ribonucleic acid (RNA) within 28 days prior to first dose. HIV test within 28 days prior to first dose

Table 5.1-1: Screening Assessments (CA209436)		
Procedure	Screening Visit	Notes (Screening procedures are to occur within 28 days from first dose unless otherwise specified)
Urinalysis	X	Total protein, glucose, blood, leukocyte esterase, specific gravity, and pH, within 14 days prior to first dose
Pregnancy Test	X	For WOCBP only and must be done within 24 hours of first dose.
Efficacy/Biomarker Assessment		
Radiographic Tumor Assessment CT chest, CT/MRI abdomen, pelvis and other known sites of disease (also required for CTCL) FDG PET-CT (DLBCL, PTCL, PMBL & MGZL only)	X	To be performed within 28days prior to first dose. Contrast enhanced CT chest, CT/MRI abdomen, pelvis and other known sites of disease. Brain MRI for CNS assessment (only if clinically indicated). Non-contrast CT chest and MRI abdomen/pelvis acceptable if CT with contrast is contra-indicated. Modality should remain the same for each subject throughout the study FDG PET-CT will be used for response assessment for DLBCL, PTCL, PMBL and MGZL only. Refer to section 5.4.3.3
Blood tumor burden assessment (SS-CTCL only)	X	Required only for CTCL Sezary Syndrome for assessment of tumor burden and baseline staging. Refer to section 5.4.3.6 and Appendix 3 for further details
Modified Severity Weighted Assessment Tool	X	Required for subjects with Cutaneous T Cell Lymphoma. Refer to Appendix 4 .
Medical Photography	X	Suggested for subjects with Cutaneous T Cell Lymphoma only. Refer to Section 5.4.3.5
CD30 Expression	X	CD30 expression \geq 1% in tumor or TILs must be confirmed by local IHC testing prior to first dose. It will also be done centrally and assessed retrospectively.
Bone Marrow Biopsy & Aspirate	See Note	Bone Marrow assessment is not required for DLBCL/CTCL/PMBL/MGZL subjects unless clinically indicated. It is recommended for PTCL subjects if there is clinical suspicion for disease involvement in the bone marrow. Refer to section 5.4.4 for further details. Only if clinically indicated, bone biopsy & aspirate collected during screening are acceptable. If a biopsy and/or aspirate is performed during treatment, submission for biomarker analyses is optional. Refer to Table 5.6-1 for further details.

Table 5.1-1: Screening Assessments (CA209436)		
Procedure	Screening Visit	Notes (Screening procedures are to occur within 28 days from first dose unless otherwise specified)
Tumor tissue submission	X	
Submission of tumor tissue (FFPE tumor tissue block or a minimum of 20 unstained slides, obtained during the screening phase or collected as a standard of care procedure prior to obtaining informed consent) is mandatory. Tumor tissue must have been collected within 20 months from screening, while slides must have been cut within 6 months from screening.
 
In order to be treated, the sample must meet the minimum quality requirements, as determined by the central laboratory during the screening period.
 
Biopsy samples should be excisional, incisional or core needle. Refer to Section 5.6.1 and also to Table 5.6-1 for further details.

Serum/plasma	X	Specification of test performed is described in Table 5.6-1
IVRS/Clinical Drug Supplies		
Phone calls to IVRS	X	
Phone calls must be made to IVRS as follows:
 
For subject number assignment at the time informed consent is obtained and trigger 1st shipment of drug. Refer to section 4.4 for further details.

Table 5.1-2: On Treatment Procedures (CA209436)				
	On treatment procedures			
Procedure	Cycle 1 Day 1	Cycle 1 Day 8	Cycle 2 & Beyond, Day 1	Notes
All windows proposed are calendar days. Procedures must be done within 72h prior to dosing unless otherwise specified.				
Safety Assessments				
Targeted Physical Examination	X		X	Include assessment of lymph node areas (eg, submandibular, cervical, supraclavicular, axillary, or inguinal lymph node), abdominal organs (eg, spleen) and neurological examination Skin evaluation using mSWAT scoring for CTCL Refer to section 5.3 for further details.
Vital Signs and Oxygen Saturation	X	X	X	Temperature, BP, HR, O ₂ saturation by pulse oximetry at rest (also monitor amount of supplemental oxygen if applicable) prior to dosing and at any time a subject has any new or worsening respiratory symptoms. Refer to section 5.3 for further details.
Adverse Events Assessment	-----Continuously-----			Assessed using NCI CTCAE v. 4.03
Review of Concomitant Medications	X	X	X	
Physical Measurements	X	X	X	Includes weight and ECOG status
Laboratory Tests		X	X	To be done within 72 hours prior to dosing and include: CBC with differential, uric acid, BUN or serum urea level, creatinine, Ca, Mg, K, Cl, Na, amylase, lipase, glucose, AST, ALT, total bilirubin, alkaline phosphatase, albumin, LDH.
Thyroid Function Testing			See Note	TSH (reflex to free T3 and free T4 if abnormal result) to be performed at every other cycle (C3, C5, etc). Refer to section 5.3 for further details.
Pregnancy Test (WOCBP only)	X		See Note	Serum or urine within 24 hours prior to first dose and then at least once every 4 weeks regardless of dosing schedule.

Table 5.1-2: On Treatment Procedures (CA209436)				
Procedure	On treatment procedures			Notes All windows proposed are calendar days. Procedures must be done within 72h prior to dosing unless otherwise specified.
	Cycle 1 Day 1	Cycle 1 Day 8	Cycle 2 & Beyond, Day 1	
Efficacy/Biomarker Assessments				
Radiographic Tumor Assessment 
 CT chest, CT/MRI of abdomen, pelvis and any other known sites of disease (required for CTCL) FDG PET-CT (DLBCL, PTCL, PMBL & MGZL only)			See Note	Tumor assessments will occur at Week 6 and Week 12 continuing every 9 weeks (+/- 1 week) for the subsequent 4 tumor assessment timepoints, regardless of dosing schedule. After the first year, tumor assessments are to occur every 12 weeks (+/- 2 weeks) until disease progression is documented. Patients with treatment beyond progression should be evaluated at minimum every 12 weeks (see appendix 2). Radiographic evaluations in subjects with CTCL will be performed as clinically indicated by the disease stage. FDG PET-CT is the method of assessment for DLBCL, PTCL, PBML & MGZL subjects. Subjects with PET-Avid lesions at baseline should be followed with PET, subjects with non-Pet avid lesions and lesions on CT scans at baseline should be followed with CT Scans. Refer to section 5.4 for further details.
Blood tumor burden assessment (SS-CTCL only)			See Note	Only required to confirm CR in CTCL SS subjects in case blood was positive for tumor cells at screening. Refer to section 5.4.3.6 .
Modified Severity Weighted Assessment Tool			See Note	Required for subjects with Cutaneous T Cell Lymphoma as part of disease assessment. To be completed at each visit. Refer to Appendix 4 for further details.
Medical Photography			See Note	Suggested for subjects with Cutaneous T Cell Lymphomas as part of disease assessment. To be done along with the radiographic assessment timepoints. Refer to section 5.4.3.5 for further details.

Table 5.1-2: On Treatment Procedures (CA209436)				
	On treatment procedures			
Procedure	Cycle 1 Day 1	Cycle 1 Day 8	Cycle 2 & Beyond, Day 1	Notes
				All windows proposed are calendar days. Procedures must be done within 72h prior to dosing unless otherwise specified.
Bone Marrow Aspirate and Biopsy			See Note	Bone Marrow assessment is not required for DLBCL/CTCL/PMBL/MGZL subjects unless clinically indicated. It is recommended for PTCL subjects if there is clinical suspicion for disease involvement in the bone marrow. If a biopsy and/or aspirate is performed during treatment, submission for biomarker analyses is optional. Refer to Table 5.6-1 for further details. Required to confirm complete response (CR) in subjects with bone marrow disease at screening.
Additional Biomarker Samples • Tumor biopsy • Blood	See Note	See Note	See Note	See Table 5.6-1 for collection of samples for biomarker studies
Outcomes Research Questionnaire				
EQ-5D 3L Questionnaire	X		X	Subjects will be asked to complete the EQ-5D 3L prior to study drug administration and before any clinical activities. Refer to section 5.7 for more information. To be completed only for subjects enrolled in the Expansion Phase (Cohort B).
PK and Immunogenicity Assessments				
PK and Immunogenicity Samples				See Table 5.6-1 for sampling details.

Table 5.1-2: On Treatment Procedures (CA209436)				
	On treatment procedures			
Procedure	Cycle 1 Day 1	Cycle 1 Day 8	Cycle 2 & Beyond, Day 1	Notes
All windows proposed are calendar days. Procedures must be done within 72h prior to dosing unless otherwise specified.				
Clinical Drug Supplies				
Administer Study Drug	Brentuximab vedotin	Nivolumab	X	
Brentuximab vedotin will be administered at C1D1 and Nivolumab will be administered on C1D8. At all subsequent cycles, both study drugs will be administered on the same day. Brentuximab vedotin will be administered first followed by a minimum 30 minute rest. Nivolumab will be administered second. Refer to Section 4.5 for further details.
 
IVRS should be called within 3 days prior to study drug administration to receive vial assignment.

Table 5.1-3: Follow-up Assessments (CA209436)			
Follow-up Assessments (CA209436)			
Procedure	Follow Up, Visits 1 and 2^a (X01 & X02)	Survival Follow-Up Visits^b	Notes
Safety Assessments			
Targeted Physical Examination	X		Lymph node areas (eg, submandibular, cervical, supraclavicular, axillary, or inguinal lymph node), abdominal organs (eg, spleen) and neurological examination Skin evaluation with mSWAT scoring in CTCL
Adverse Events Assessment	X		
Laboratory Tests	X		Required for X01: CBC with differential, uric acid, serum urea level, serum creatinine, sodium, potassium, calcium, magnesium, chloride, glucose, AST, ALT, total bilirubin, alkaline phosphatase, LDH, TSH (reflex to free T3, free T4 for abnormal TSH result). Panel should also be performed at X02 if X01 results were abnormal.
Pregnancy Test (WOCBP only)	X		Serum or urine

Table 5.1-3: Follow-up Assessments (CA209436)			
Follow-up Assessments (CA209436)			
Procedure	Follow Up, Visits 1 and 2^a (X01 & X02)	Survival Follow-Up Visits^b	Notes
Efficacy Assessments			
Radiographic Tumor Assessment CT chest, CT/MRI abdomen, pelvis, and any other known sites of disease FDG PET-CT (DLBCL, CTCL, PMBL & MGZL only)	X	X	Only for subjects without documented progression since first dose of study therapy Tumor assessments will occur at Week 6 and Week 12 continuing every 9 weeks (+/- 1 week) for the subsequent 4 tumor assessment timepoints, regardless of dosing schedule. After the first year, tumor assessments are to occur every 12 weeks (+/- 2 weeks) until disease progression is documented. FDG PET-CT is required for assessment of DLBCL/PTCL/PMBL/MGZL subjects NOTE: Subjects proceeding to allogeneic SCT or ASCT will be assessed on Day 100, at 6 months, 1 year and every year thereafter from the date of stem cell infusion until the first non-CR after SCT is documented. Refer to section 5.4 for further details.
Blood tumor burden assessment (SS-CTCL only)	See note	See note	Only required to confirm CR in CTCL SS subjects in case blood was positive for tumor cells at screening. Refer to section 5.4.3.6 for details.
Modified Severy Weighted Assessment Tool for subjects with Cutaneous T Cell Lymphoma	See note	See note	Required for subjects with Cutaneous T Cell Lymphoma as part of disease assessment. Refer to Appendix 4 for details.
Medical Photography	See note	See note	Suggested for subjects with Cutaneous T Cell Lymphomas as part of disease assessment. To be done along with the radiographic assessment for all of those respective timepoints. Refer to section 5.4.3.5 for details.

Table 5.1-3: Follow-up Assessments (CA209436)			
Follow-up Assessments (CA209436)			
Procedure	Follow Up, Visits 1 and 2^a (X01 & X02)	Survival Follow-Up Visits^b	Notes
GVHD Assessments			Only for subjects who proceed to allogeneic SCT. To be assessed on Day 100, at 6 months, at 1 year and every 1 year thereafter from the date of stem cell infusion until the first non-CR after SCT is documented. Refer to Appendix 5 for further details.
Subsequent Anticancer Therapy	X	X	
Other Primary Malignancies	X	X	
Biomarker Assessments			
Serum, Tumor Biopsy, Bone Marrow Aspirate/biopsy	See Note		Optional biomarker samples collected at time of progression. See Table 5.6-1 for biomarker sampling details
Pharmacokinetic/Immunogenicity Assessments			
PK and Immunogenicity samples	X		See Table 5.5.1-1 for PK and immunogenicity sampling details
Outcomes Research Assessments			
EQ-5D 3L Questionnaire	X	X	EQ-5D-3L questionnaires administered during survival follow-up will be completed in clinic or via phone contact. Refer to section 5.7 for more information. To be completed only for subjects enrolled in the Expansion Phase (Cohort B).

Table 5.1-3: Follow-up Assessments (CA209436)			
Follow-up Assessments (CA209436)			
Procedure	Follow Up, Visits 1 and 2^a (X01 & X02)	Survival Follow-Up Visits^b	Notes
Subject Status			
Survival Status	X	X	Survival follow-up visits are expected to occur every 3 months after X02; may be accomplished by visit, phone contact or email, to update survival information and assess subsequent anti-cancer therapy. BMS may request that survival data be collected on all treated subjects outside of the 3 month specified window. At the time of this request, each subject will be contacted to determine their survival status unless the subject has withdrawn consent for all contact.

^a Follow-up visit 1 (X01) = 35 days from the last dose +/- 7 days. Follow-up visit 2 (X02) = 80 days (+/- 7 days) from follow-up visit X01.

^b Survival Follow-up visits to occur every 3 months from X02. BMS may request that survival data be collected on all treated subjects outside of the 3 month specified window. At the time of this request, each subject will be contacted to determine their survival status unless the subject has withdrawn consent for all contact.

